16. DEFINITION OF ADVERSE EVENTS

16.1. Serious Adverse Event (SAE)

Serious Adverse Event (SAE): An Unanticipated Adverse Device Effect associated with the device (UADE) is considered to be "serious" in any of the following categories and should be reported to OnPoint Vision Inc. OnPoint Vision Inc. within 5 working days after the investigator first learns of the event.

- Results in death
- Life-threatening
- Hospitalization greater than 24 hours
- Persistent and/or significant disability/incapacity
- Sight-threatening

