16.2. Intraoperative Ocular Adverse Events

- Hyphema
- PCIOL Dislocation
- Retinal Tear
- Vitreous/Subchoroidal Hemorrhage
- Vitrectomy
- Retinal Detachment
 - Rhegmatogenous Retinal Detachment
- Ruptured Capsular Bag with or without Vitrectomy
- Ruptured or Damaged Zonules
- PCIOL Lens Dislocation from the Bag
 - Partial
 - Complete
- Excessive length of time in the eye to deliver (longer IOPCL AMD-MAG than 30 minutes)
- Failure to Implant IOPCL

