17. ADVERSE EXPERIENCE AND COMPLICATION REPORTING

Throughout the course of the proposed study, all efforts will be made to remain alert to possible adverse experiences or untoward findings. If adverse experiences occur, the first concern will be the safety and welfare of the subject and appropriate medical intervention will be made. Any adverse experiences observed by the investigator or reported by the subjects, whether or not ascribed to the investigational procedure or device, will be recorded on the subject's adverse event case report form. A new adverse event case report form is used for each adverse event or adverse event-related visit.

Any serious adverse events (SAEs) and unanticipated adverse device events (UADE), whether ascribed to the investigational device or not, will be communicated as soon as possible to OnPoint Vision Inc. and to the IRB. These reports must be confirmed in writing within 5 working days of learning of the occurrence. Any subjects who are terminated from the study due to adverse experiences will be followed and documented until their medical outcome is determined, and a written report provided to OnPoint Vision Inc. by the investigator.

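### Protocol 16.1 defines a serious adverse event as a subset of unanticipated device effects, which conflicts with Section 17 and leaves expedited reporting of some serious events ambiguous

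*Protocol*

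**What the plan says.** Protocol 16.1 is headed Serious Adverse Event, but the subject of its defining sentence is a UADE: "An Unanticipated Adverse Device Effect associated with the device (UADE) is considered to be" serious when it falls into one of five categories. These are death, threat to life, hospitalization beyond 24 hours, lasting or significant disability, and "Sight-threatening". Such an event is to reach the sponsor "within 5 working days after the investigator first learns of the event".

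Protocol 16.2 and 16.3 then list intraoperative and postoperative ocular adverse events. The lists include "Ruptured Capsular Bag with or without Vitrectomy", vitrectomy, retinal detachment and endophthalmitis.

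Protocol 17 sets the reporting rule, with this scope: "adverse events (SAEs) and unanticipated adverse device events (UADE), whether ascribed to the investigational device or not, will be communicated as soon as possible". The recipients are the sponsor and the IRB. On timing it adds: "These reports must be confirmed in writing within 5 working days of learning of the occurrence". It also requires every adverse experience to be documented, "whether or not ascribed to the investigational procedure or device, will be recorded on the subject's adverse event case report form". Section 19 has completed forms scanned to the sponsor within seven days of the study visit.

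Protocol 4.2 says that suspension will be considered after at least two consecutive severe ocular injuries at one site that are related to the surgery and/or the device. SAP 7.5.6 tabulates each adverse event by visit and over the study, with no separate summary of serious events.

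**The concern.** An SAE definition should rest on how bad the event is. Whether the event was expected, and whether the device caused it, are separate questions. Section 16.1 builds both into the definition. An investigator who applies it as written could conclude that a capsular rupture caused by the surgery, or an endophthalmitis that the protocol already names, is not an SAE. Section 17 does not settle the matter: it uses the term SAE without defining it, so the reader goes back to 16.1.

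At stake is the route and speed by which serious events reach the sponsor and the IRB in an early feasibility study of an implant. The injuries that feed the suspension rule in 4.2 are of the kind whose SAE status is unclear. One of the two examples given there, posterior capsule rupture with lens dislocation leading to vitrectomy during surgery, overlaps with entries in the 16.2 list.

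**Working it through.** No arithmetic underlies the plan's wording, so the check sets the sections side by side.

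**1. Definition, scope, recipients, clock**

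| | Protocol 16.1 | Protocol 17 | Case report forms (Protocol 17 and 19) |
|---|---|---|---|
| Events covered | UADEs meeting a seriousness category | SAEs and UADEs, as two classes | All adverse experiences |
| Attribution | Associated with the device | Irrelevant | Irrelevant |
| Anticipation | Unanticipated only | Not addressed for SAEs | Irrelevant |
| Recipients | Sponsor | Sponsor and IRB | Sponsor |
| Clock | 5 working days from learning of the event | As soon as possible; in writing within 5 working days of learning | Seven days from the visit |

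The two expedited clocks agree. Scope and recipients do not.

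**2. A sight-threatening event under each reading**

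Assume that an event named in 16.2 or 16.3 may be regarded as anticipated.

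| Event | 16.1 as written | 17, taking SAE from 16.1 | 17, taking SAE as any event meeting a seriousness category |
|---|---|---|---|
| Not listed, device-associated | SAE | Expedited | Expedited |
| Not listed, procedure-related only | Not an SAE | Contradictory: the definition excludes it, the attribution clause includes it | Expedited |
| Listed, device-associated | Not an SAE | Not expedited | Expedited |
| Listed, procedure-related only | Not an SAE | Not expedited | Expedited |

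Only the first row gives the same answer throughout. The second row conflicts whatever anticipated means, because 16.1 requires association with the device and Section 17 sets attribution aside. Rows three and four turn on anticipation, where Section 17 is silent: it expressly lifts the attribution limit ("whether ascribed to the investigational device or not, will be communicated as soon as possible") and no other.

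**3. How far the case report form route fills the gap**

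If the investigator learns of the event at a visit, the difference in timing is small: 5 working days plus a weekend is 5 + 2 = 7 calendar days. What is then missing is the immediate communication and the IRB notice.

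If the event becomes known between visits, the form clock has not started. From the windows in Protocol 14, the Form 4 and Form 5 visits can be 330 − 180 = 150 to 420 − 120 = 300 days apart. An interim visit under 14.2 would shorten this, and one is likely after a serious event, so 150 to 300 days is the spacing of scheduled visits and not an expected delay.

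**4. Link to the suspension rule**

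Protocol 4.2 counts injuries related to the procedure and/or the device. Section 16.1 covers device-associated effects only. Procedure-related injuries therefore count towards suspension but are not SAEs under 16.1.

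**The case against.** The strongest reply is that Section 17 already works. It names SAEs and UADEs separately, which would be redundant if one were a subset of the other, and its attribution clause makes sense only if SAE has its ordinary meaning. On that reading a serious listed event is reported to the sponsor and IRB within 5 working days. This is a fair reading, and perhaps the intended one. But it requires the investigator to set aside the only definition that the protocol gives, so the conflict stands.

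Other parts of the defence limit the point:

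- A reader might infer that listed serious events escape expedited reporting. The documents do not establish this; Section 17 may capture them.
- A reader might infer that everything in 16.2 and 16.3 falls outside the SAE definition. Neither list is labelled anticipated, unanticipated is not defined, the 16.3 list includes an open Other category, and many entries would not be serious in any case.
- A reader might treat a missed expedited report as an unreported event, one eye in ten. Every adverse experience is recorded and sent to the sponsor, so the issue is route, timing and IRB notice. The fraction 1/10 measures no effect of the wording.
- A reader might expect such events to be missing from an SAE count. The SAP plans no such count; 7.5.6 tabulates events whatever their seriousness, and 7.5.3 lists each secondary surgical intervention.
- The suspension rule uses its own term with its own definition, and the sponsor or investigator can suggest suspension at any time. The wording of 16.1 does not change what counts there. It bears only on how promptly and by what route the sponsor hears.

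**Conclusion.** The point holds as an inconsistency between Protocol 16.1 and 17. Section 16.1 as written restricts SAEs to unanticipated, device-associated effects; Section 17 treats SAEs as a separate class, disregards attribution and adds the IRB. For sight-threatening events that are procedure-related, or that an investigator could regard as anticipated, use of the 5-working-day sponsor and IRB route is ambiguous. It has not been shown that these events would miss that route.

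There is no numerical size: no estimate, rate or planned table changes. The practical weight comes from the setting. With at most 10 eyes at three sites, and a suspension trigger of two consecutive injuries at one site, each report counts.

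The conflict over attribution and recipients rests on the text alone. The part about listed events also assumes that naming an event in 16.2 or 16.3 lets an investigator regard it as anticipated, which is natural but not stated. The case report forms and the investigator responsibilities (Appendices 8 and 5) were not available, so whether the adverse event form captures seriousness independently of UADE status could not be checked.

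**What to change.** Reconcile the two sections:

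1. In 16.1, define an SAE as any adverse event that meets one of the listed seriousness categories, whether or not it was anticipated and whatever its attribution.
2. Define UADE separately, and say what makes an event unanticipated, including whether appearing in 16.2 or 16.3 bears on it.
3. Have Section 17 cite both definitions, and give the same recipients (sponsor and IRB) and the same clock in both places.
4. Optionally, add an SAE listing to SAP 7.5.6. With at most 10 eyes this is mainly a convenience for the reader, since all events are already tabulated.

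The cost is a few sentences of protocol wording, one optional listing, and slightly more expedited reports.

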16.2. Intraoperative Ocular Adverse Events

- Hyphema
- PCIOL Dislocation
- Retinal Tear
- Vitreous/Subchoroidal Hemorrhage
- Vitrectomy
- Retinal Detachment
 - Rhegmatogenous Retinal Detachment
- Ruptured Capsular Bag with or without Vitrectomy
- Ruptured or Damaged Zonules
- PCIOL Lens Dislocation from the Bag
 - Partial
 - Complete
- Excessive length of time in the eye to deliver (longer IOPCL AMD-MAG than 30 minutes)
- Failure to Implant IOPCL

16.3. Postoperative Ocular Adverse Events

Endophthalmitis

- Toxic Anterior Segment Syndrome (TASS)
- Chronic Anterior Uveitis
- Hyphema
- Hypopyon
- Implantable Pseudophakic Contact Lens Dislocation
- Cystoid Macular Edema
 - Clinically Significant Cystoid Macular Edema with reduction in BCDVA of 20/40 or worse at Form 3 (1-2 months post op) or later
- Pupillary Block
- Mechanical Pupillary Block
- Retinal Detachment
 - Rhegmatogenous Retinal Detachment
- Malpositioned/Misaligned Optics (IOPCL not centered over PCIOL and with unequal leaflet coverage of all IOPCL haptic tabs, or IOPCL tilted away from the PCIOL and without anterior leaflet coverage)
 - Early onset: occurring prior to Form 4 visit window (i.e., < 120 days)
 - o Late onset: occurring \ge 120 days
- Unseated IOPCL haptic tabs (One or more haptic tabs not securely attached to the PCIOL)
- Lens Optical Performance
- Mechanical Failure (Tear in haptic tab)
- Vitreous Aspiration for Pupillary Block
- Corneal Stroma Edema
 - o Corneal Edema with BCDVA of 20/40 or worse at Form 3 (1-2M post-op) or later
- Iritis present at 1-month or later
- Macular Edema present at 1-month or later
- Raised IOP requiring treatment
 - o Raised IOP, greater than 10 mmHg above baseline or greater than or equal to 25 mmHg.
- Iris Chafing
- Iris Trauma
- Iris Transillumination Defects

- Pigment Dispersion
- Pseudophacodonesis or Evidence of Zonular Trauma/Dehiscence
- Inter-device opacification or fibrosis between the PCIOL and IOPCL
- Ruptured capsular tissue
- Patient Reported Symptoms described as severe.
- Inability to go down steps, stairs or curbs in dim light or at night due to postoperative vision
- Inability to notice objects in the periphery while walking due to postoperative vision
- Other

Note: Secondary Surgical Intervention(s) (SSI) may be necessary to resolve any of the adverse events identified above. If an SSI is conducted in the trial, the details of the SSI and corresponding reason for SSI will be documented on the SSI CRF.

Examples of Secondary Surgical Interventions

- Irrigation of IOPCL/PCIOL Interface
- IOPCL Exchange
- Reposition of the same Implantable Pseudophakic Contact Lens
- IOPCL Removal
- Iridectomy for Pupillary Block

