4.1. Safety Endpoints

- Preservation of BCDVA Proportion of eyes (< 5%) that lose two or more lines of BCDVA (≥10 letters on the ETDRS chart) at 12 months from baseline.
- Preservation of BCNVA Proportion of eyes (<5%) that lose two or more lines of BCNVA
 (≥10 letters on the Sloan Near Vision Chart at 14 cm) at 12 months from baseline.
- Incidence of secondary surgical intervention (SSI).
- Successful delivery of the IOPCL AMD-MAG as determined at all postoperative scheduled visits starting at 7-14 days post-operative.
 - No capsular tear
 - No visible damage to either the PCIOL or the IOPCL AMD MAG
 - o Uniform leaflet coverage of all IOPCL AMD MAG haptic tabs
- Long-term adherence and positional stability
 - O Gap: Minimal change in uniformity of the gap between consecutive scheduled visits at 1-2 months and later as determined by UBM measurements. Minimal change is defined as +/- 10 microns between visits is established and maintained using UBM imaging.
 - o Tilt:
- Tilt of the PCIOL as determined at all post-operative scheduled visits starting at 30-60 days post-operative. Minimal tilt of the PCIOL confirmed via penlight examination and defined as ≤ 10 degrees between the postoperative tilt of the PCIOL and the pre-operative tilt of the PCIOL.
- Tilt of the IOPCL AMD-MAG as determined at all post-operative scheduled visits starting at 30-60 days post-operative. Minimal tilt of the IOPCL AMD-MAG (using the PCIOL as a reference point) confirmed via penlight examination and defined as ≤ 10 degrees between the post-operative tilt of the. PCIOL and the postoperative tilt of the IOPCL AMD-MAG.
- O Decentration: Decentration as determined at all post-operative scheduled visits starting at 7-14 days post-operative. Centration of the IOPCL AMD-MAG (using the PCIOL as a reference point) confirmed during slit lamp examination and defined as uniform exposed area of the PCIOL outside of the IOPCL AMD-MAG at the vertical and horizontal meridians between ≥ 0.25 mm and ≤ 0.75 mm.
- Counts and percentages for incidence of cumulative and persistent intraoperative and post-operative adverse events
- Counts and percentages for incidence of secondary surgical interventions (e.g., removal
 of interlenticular opacity, repositioning of IOPCL, explant of IOPCL, repositioning of
 PCIOL) (excluding Nd:YAG treatments for PCO).

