5. SUBJECT POPULATION

A maximum of 10 pseudophakic eyes in subjects with a diagnosis of age-related macular degeneration will be implanted unilaterally with the IOPCL AMD-MAG. All ocular eligibility criteria refer to the study eye only.

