5.1. Inclusion Criteria

- 1. Subjects aged 55 years or older.
- 2. Subjects who have already had cataract surgery with an Alcon SN60WF, SA60AT or SA60WF monofocal intraocular lens with a lens power between 17.0 diopters and 24.0 diopters clearly evidenced by photographic documentation by one of the following:
 - patient medical record
 - clinic chart with labeling attached
 - surgical record with labeling attached, or
 - patient identification card with make, model and serial number.
- 3. Subjects who have already had cataract surgery at least 6 months from the planned date of the IOPCL surgery.
- 4. Subjects with non-neovascular dry AMD or stable wet AMD meeting the following criteria:
 - No macular fluid retention in the past 12 months
 - No treatment within the past 12 months
 - No change in Amsler Grid test within the past 12 months
 - No subretinal fluid or macular hemorrhage confirmed by optical coherence tomography (OCT) imaging.
 - No fundoscopic changes within the past 12 months (i.e., changes in retinal pigment epithelium).
- 5. Subjects with best corrected distance visual acuity from 20/80 to 20/800.
- 6. Subjects with a preoperative manifest refraction spherical equivalent (MRSE) of +1.0D to -1.0D.
- 7. Subjects with ≤1.0D of corneal cylinder determined by keratometry readings.
- 8. Subjects who are unsatisfied with their current near vision correction provided by either spectacles or external magnifier.
- 9. Subjects who have experienced and failed one or more high-magnification refractive correction alternatives to the IOPCL AMD-MAG.

- 10. Subjects who demonstrate at least 10 letters of near visual acuity improvement with the simulation/tolerance test (using manifest refraction with +7.0D add) compared to conventional near vision testing (using manifest refraction with +3.0D add).
- 11. Subjects with a minimum endothelial cell count of 1800 cells/mm².
- 12. Subjects willing to abstain from pursuing any other surgical vision-correcting procedures for the duration of the study.
- 13. Subjects who are willing and able to complete all required postoperative visits.
- 14. Subjects who are able to comprehend and sign a statement of informed consent.

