# 6.2 Sample Size

Sample size is limited to maximum of 10 subjects (eyes) for this Early Feasibility Study (EFS).

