## 7.5.6 Adverse Events

For each adverse event, number and percent of eyes reported with the event will be summarized at each scheduled visit (including intraoperatively) and during the study (i.e. cumulative and persistent).

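### The 20/40 acuity cut-off in the two edema sub-categories of Protocol Section 16.3 cannot grade visual significance, because every eligible eye enters the trial already beyond it

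*Protocol*

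**What the plan says.** Protocol Section 16.3 lists CME and corneal stromal edema as postoperative ocular adverse events and gives each one a sub-category with an acuity condition:

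- CME: "Clinically Significant Cystoid Macular Edema with reduction in BCDVA of 20/40 or worse at Form 3 (1-2 months post op) or later"
- Corneal edema: "Corneal Edema with BCDVA of 20/40 or worse at Form 3 (1-2M post-op) or later"

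The CME line contains the word *reduction* but states no amount. The corneal line refers to neither a reduction nor a baseline. The same list has a separate entry with no acuity condition: "Macular Edema present at 1-month or later".

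Protocol Section 5.1, criterion 5, sets the entry range: "Subjects with best corrected distance visual acuity from 20/80 to 20/800". Section 5 settles which eye that means: "All ocular eligibility criteria refer to the study eye only".

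The analysis is a count. SAP 7.5.6 says: "For each adverse event, number and percent of eyes reported with the event will be summarized at each scheduled visit", and adds cumulative and persistent totals. It does not grade edema further by acuity.

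**The concern.** A fixed acuity level can identify edema that costs vision only if the eye would see better than that level without the edema. In this population no eligible eye does. The sub-categories look like a severity grade, and a reader of the safety tables will take them as one. Applied as written, they do not show whether an eye with edema lost any vision.

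What is at stake is how two rows of the adverse-event table are interpreted. The corneal row would count eyes with unchanged acuity as if edema had affected their vision. The CME row would depend on how each of the three sites reads an ambiguous phrase. SAP Section 4 plans an IDE application on clinical outcomes around the 4-6 month visit, and SAP 6.8 places an interim analysis there. The counts may therefore be read before 12-month acuity is complete.

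**Working it through.** The plan gives no figure on this point to reproduce. The check compares the cut-off with the entry range and then applies each definition.

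**Inputs.** Cut-off 20/40 (Protocol 16.3); entry range 20/80 to 20/800 (Protocol 5.1, criterion 5); acuity-loss threshold of 10 ETDRS letters from baseline (Protocol 4.1); at most 10 eyes (SAP 6.2).

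**Conversion.** logMAR = log10(denominator / 20). Letters = 50 × difference in logMAR, that is, 5 letters per 0.1 line.

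| BCDVA | logMAR | Letters worse than 20/40 |
|---|---|---|
| 20/40 (cut-off) | 0.301 | 0 |
| 20/80 (best eligible eye) | 0.602 | 50 × (0.602 − 0.301) ≈ 15 |
| 20/800 (worst eligible eye) | 1.602 | 50 × (1.602 − 0.301) ≈ 65 |

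The whole entry range lies beyond the cut-off, by 3 to 13 lines. To fall outside it, an eye with edema would have to gain more than 15 letters from 20/80, or more than 65 from 20/800. Reaching 20/32 (logMAR 0.204), the first line better than 20/40, takes 50 × (0.602 − 0.204) ≈ 20 letters from 20/80 and 50 × (1.602 − 0.204) ≈ 70 from 20/800.

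**Corneal edema.** An eye that holds its entry acuity meets the acuity condition with a loss of zero letters. What remains is corneal edema at Form 3 or later.

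**CME.** The phrase has three possible readings:

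| Reading | Who meets it |
|---|---|
| BCDVA is at the level 20/40 or worse | Every eligible eye that holds its entry acuity |
| BCDVA falls across 20/40 | No eligible eye, since none starts better than 20/40 |
| BCDVA falls by any amount and ends at 20/40 or worse | Any eye with a fall, even of 1 letter |

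The third reading does exclude an eye with no loss, but the word *reduction* does that work and the 20/40 figure adds nothing.

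**Does a baseline-referenced rule discriminate?** A loss of 10 letters is 0.2 logMAR, so the denominator is multiplied by 10^0.2 ≈ 1.585. The threshold becomes about 20/127 for an eye entering at 20/80, 20/317 from 20/200, 20/634 from 20/400 and 20/1268 from 20/800. It moves with the eye, so it can separate loss from no loss across the entry range.

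**Do other planned outputs supply the missing grade?**

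- The BCDVA safety endpoint counts eyes that "lose two or more lines of BCDVA (≥10 letters on the ETDRS chart) at 12 months from baseline". It is fixed at 12 months and not linked to edema, so a loss at Form 3 or 4 that later recovers does not appear in it.
- SAP 7.5.1 offers a listing of eyes that lost two or more lines from their best earlier BCDVA, but only if needed.
- The by-visit BCDVA table in SAP 7.5.7.1 has a single open category beyond 20/80, so nearly the whole entry range shares one bin. A drop from 20/100 to 20/400 would not show.

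**The case against.** The strongest reply is that little depends on these labels, and most of it stands.

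- No edema is missed. The parent entries for CME and corneal stromal edema, and the entry for macular edema at one month or later, carry no acuity condition and are counted under SAP 7.5.6.
- The timing condition works. Both sub-categories require Form 3 or later, so they still separate persistent from early postoperative edema.
- No decision rule uses the grade. The adverse-event endpoint is descriptive, with no threshold. The stopping rules in Protocol Section 4.2 turn on severe ocular injury or on explantation for visual intolerance.
- With at most 10 eyes, the sponsor can match edema to acuity change eye by eye.

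The last point is only partly an answer. Such matching is not in the plan, and under SAP Sections 1 and 6.1 an unplanned regrading would be reported as post hoc or as a change to the planned analysis.

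A reader might go further and infer that the edema rates are either inflated throughout or forced to zero. The documents do not support that. Edema before Form 3 cannot enter either sub-category, zero arises only under the crossing reading of the CME line, and the third reading leaves out an eye with no loss. Nor can it be said that sites will in fact classify differently: the Clinical Methods and Case Report Forms (Appendices 3 and 8) are listed but are not in the text reviewed, and may clarify the wording. Finally, one misclassified eye in 10 moves a rate by 10 percentage points, but that is true of any yes/no item at this sample size and is not evidence for this point.

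**Conclusion.** The point holds as a defect in grading, not in detection. The 20/40 condition is met at entry by 100% of the eligible range, with a margin of about 15 to 65 letters. The defect is complete for corneal edema. For CME it is an ambiguity in which 20/40 never discriminates and no minimum fall is stated. Its reach is the visual-significance label in the descriptive counts of SAP 7.5.6, so it is moderate: worth correcting before events are classified, but no threat to an endpoint or a stopping rule.

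The number of eyes that would be misgraded cannot be estimated, because the documents give no expected edema rate. It could be none.

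The conclusion assumes that eyes are enrolled within criterion 5 and that the standard letter conversion applies. An eye enrolled by deviation with better acuity, or one that gains more than 15 letters despite edema, would be an exception but would not change the result.

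**What to change.** In Protocol Section 16.3, replace the 20/40 condition in both sub-categories with a loss from the eye's own preoperative BCDVA at Form 3 or later. A natural candidate is the 10 or more ETDRS letters already used in Section 4.1. The sponsor should confirm the number, since that threshold was set for a 12-month endpoint and would here apply from Form 3. Section 16.3 already defines raised IOP partly by change from baseline, so the approach is not new to this list.

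Keep the parent categories as they are, so that SAP 7.5.6 reports edema both with and without the stated loss. If comparison with other lens studies is wanted, keep the 20/40 count as a separate line. Align the Case Report Form if it carries the same wording.

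The cost is wording only: Protocol Section 15 already schedules BCDVA preoperatively and at Forms 2 to 5. The downside is that edema costing fewer letters than the threshold, for example 5 to 9 letters under a 10-letter rule, would be counted only under the parent category.
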